2.2. Eligibility criteria and subgroups

Participants will be identified by specialists in neurology and rehabilitation from inpatients at the Department of Acute Care, Department of Neurology, Thomayer University Hospital or University Hospital Kralovske Vinohrady, Prague, Czech Republic.

Inclusion criteria: Adults (18 - 85 years) after the first ischemic stroke in early sub-acute phase (40, 41), with a slight to moderately severe disability [2 - 4 on the Modified Rankin Scale (42)],

with minimal or moderate motor deficit of upper or lower extremities (on NIHSS Item 5 or 6 scores 1–3 points) who were able to perform activities of daily living prior to stroke event [0 – 2 on the Pre-Stroke Modified Rankin Score (43)], with a potential to accept 4 hours of comprehensive rehabilitation per day and to profit from the physiotherapy. Czech is their native language or its knowledge is at the level of the mother tongue.

Exclusion criteria: Low level of consciousness (vegetative state and/or minimally conscious state); severe cognitive decline that would interfere with administration of the tests, premorbid illiteracy, severe visual and/or auditory deficit that would prevent proper completion of the tests; behavioural disorders and/or lack of cooperation with therapist; and severe medical problems with a poor prognosis, (e.g., severe frailty, advanced and incurable cancer, fracture, cardiovascular disorders as chronic heart failure NYHA III, IV, symptomatic coronary artery disease Angina Severity Class III, IV, respiratory insufficiency as chronic obstructive pulmonary disease GOLD IV, and other severe disease) (44).

Randomisation

All patients meeting the above criteria will be invited to participate and asked to provide a written informed consent. They will be randomly assigned (1:1:1:1) as soon as possible, but always within 48 hours of admission, into one of the four interventions (represented by Group 1, 2, 3 or 4) using offsite-independent randomization protocols (www.randomization.com). Concealed allocation will be performed using sequentially numbered opaque sealed envelopes only accessible by research personnel with no involvement in the trial.

2.3. A detailed description of four groups

Three groups in intervention cohorts will receive the same length of rehabilitation, i.e., 4 hours per day. Therapists in each group will be maximally helpful and will adopt a schedule for each patient to complete all the sessions. The treatment in each session will be led in person by well-educated, experienced therapists specially trained in each method. The treatment will be modified according to the patient's status and reaction to the therapy. Physical load during all therapies will be perceived maximally as a moderate level of intensity [12 - 14 on the Borg Scale (45)]. Information about the treatment will be recorded using codes of Public Health Insurance, Czech Republic (codes correspond to The Current Procedural Terminology code set system).

Group 1: COMprehensive Intensive REhabilitation Program after STROKE implementing the ICF concept (COMIRESTROKE – ICF)

This interventional arm suits the purposes of setting individual goals of the therapy which take account of the given situation of the rehabilitated person (46-48). The ICF system establishes a common health language to articulate human functioning across the lifespan and from individual to population health settings system (49, 50). On the individual level, functioning is considered as an interaction between a health condition and the contextual factors facilitating or acting as a barrier for functioning (51). Focusing on patient's quality of life and participation domain of the ICF applies a paradigm shift in neurorehabilitation research design (52). Engagement in valued activities was found to be significantly associated with subsequent improvement in emotional well-being (53).

Patients randomized to the GROUP 1 will undergo a multidimensional assessment, a functional profile will be created and the individual goals and intervention proposed and defined throughout the ICF framework. Clinical application can be rather arduous (54) and sharing of the feasibility experience is highly valued. This study arm design follows recommendations and

experience with implementation of the ICF model into clinical practice in rehabilitation in people after stroke (55).

Limiting the burden of iterative processing the proposed battery of clinical examinations, questionnaires surveys and filling out the ICF core set documentation which is then used to compile "ICF Categorical Profile", this study proposes a direct linking of some clinical test results to the codes included in the Comprehensive ICF core set for stroke used (56). Linking of normal-range clinical examination results may ease the procedure. Linking will take place regarding specified items from the test battery: WHODAS 2.0 (57) NIHSS, mRS, MoCA (58), MAL (59), FIM, BBS (60), TUG, NHPT, ARAT, GSS, 3F test, MAST. Overlapping items will be further discussed.

The clinical assessment involves the following three steps: 1) description of patient's problems and resource; 2) setting of mutually agreed goals, based on the functional profile; 3) and determination of intervention targets. The interdisciplinary team together with the patient will use the functional profile to define in detail the overall goal and sub-goals, and to determine specific therapeutic interventions to achieve them (42). Participants in this group will undergo four hours of treatment per day (the same time as in the remaining two cohorts), but the time spent with each specialist will depend on the individually set goals. The "ICF Intervention Table" will be used to monitor and evaluate the work during individual targeted interventions and will also serves as a means of communication between the members of the interdisciplinary team. The team will meet weekly to provide feedback, evaluate the fulfilment of the set goals and to adjust therapeutic procedures so that the goals of the therapy are best met.

After the end of the intensive complex inpatient program COMIRESTROKE – ICF, as the continuum of care, participants will be referred and to a short-term outpatient rehabilitation programme.

Group 2 and 3

Participants will undergo COMprehensive Intensive REhabilitation Program after STROKE routinely offered at the Department of Rheumatology and Rehabilitation, Third Faculty of Medicine, Charles University and Thomayer University Hospital (39) three hours per day. In the program, the multidisciplinary team of practitioners from different clinical fields (physiotherapy, occupational therapy, clinical speech therapy and psychology) will be led by a medical doctor, a specialist in rehabilitation and physical medicine. Efforts of the different team members are parallel and discipline oriented.

In addition, participants in these two groups will undergo one hour of physiotherapy per day. **Group 2:** COMprehensive Intensive REhabilitation Program after STROKE implementing technology-based physical PT (COMIRESTROKE – TECH) Participants will receive a technology-based PT that follows the principles of sensorimotor learning, i.e. repeated specific and targeted functions in different environments / conditions in order to strengthen the memory footprint and initiate structural changes in the CNS. According to the indication, participants will be offered one of the robotic systems using an exoskeleton (Gloreha, Erigo and Meditutor) or a therapy using a virtual environment (61, 62).

Group 3: COMprehensive Intensive REhabilitation Program after STROKE implementing neuroproprioceptive "facilitation and inhibition" physiotherapy (COMIRESTROKE – NEFI). Participants will receive an individual neuroproprioceptive "facilitation, inhibition" PT (Vojta reflex locomotion, Bobath concept), where appropriate stimuli in a suitable time sequence are combined with the aim to maintain optimal motor pathway function and ability control (63, 64). After finishing this intensive complex inpatient program COMIRESTROKE, participants will undergo standard/not directed treatment offered by the Czech Health Care system. Information

as to the health and social care the rehabilitant received after hospitalisation will be collected by phone call.

Group 4: A comparative group will undergo standardly provided care at department of neurology including face to face physiotherapy (bed mobility, transfers, gait, therapeutic exercises, positioning, education).

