2.5. Outcomes and measures

2.5.1. Primary Outcomes

- PROMIS Global Health is a 10-item scale which asks the patient to assess (self-report) their physical, mental and social health in the past 7 days (72, 73).
- WHODAS 2.0 is a generic assessment instrument developed by WHO to provide a standardized method for measuring health and disability. It is grounded in the conceptual framework of the ICF and integrates an individual's level of functioning in major life domains and directly corresponds with ICF's "activity and participation" dimensions. The 36-item version will be used. Higher score means higher disability (74).
- GAS is an individualized outcome measure involving goal selection and goal scaling that is standardized in order to calculate the extent to which patient's goals are met. Each goal is rated on 5-point scale (-2 much less than expected, 0 achieved the expected level, 2 much more than expected (75, 76).

Three types goals will be established:

A. Overarching long-term goal (Global Goal, G) that reflects a desired improvement on the level of participation: usually restoration of previous life including remunerative employment, sport and leisure activities (interview by call at 3 and 12 months follow up).

B. Mid-term goal (Program Goal, P) that reflects improvement mainly in the domain of activities and participations achievable by the rehabilitation program: restoration of self-care, (almost) independence in daily living etc. (interview by call at 3 months follow up)

C. Three Short-term goals (Cycle Goals C1, C2, C3) mainly in the domain of functioning and activities. Usually specific, most problematic components of the Program Goal (evaluated by the rehabilitation team together with the rehabilitant).

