2.8. Hypotheses

This clinical trial will test the following scientific hypotheses:

I. COMIRESTROKE under all three settings has a positive influence on all outcomes and higher effect than control group.

II. COMIRESTROKE - ICF will have the highest impact on primary outcomes (GAS, PROMIS, WHODAS 2.0) and on such secondary outcomes that were identified as treatment goals. Furthermore, we expect the highest impact on the primary outcomes in the follow-up (three and twelve months after finishing the rehabilitation).

III. COMIRESTROKE – NEFI will have the highest effect on the secondary outcomes, mainly on motor functions. Moreover, it will most significantly lead to the initiation of plastic and adaptive processes, assessed by the level of lncRNAs in the peripheral blood.

IV. The most important predictor of effective rehabilitation will be the level of disability at admission time; however, the content of the rehabilitation will have an impact on perceived, clinical, and physiological changes of the rehabilitant.

The exploratory goals of this clinical trial are as follows:

Goal I - Improvement patterns: Considering the high number of measured outcomes, for a deeper understanding of therapy efficacy with respect to patient and treatment characteristics, this clinical trial will aim to identify groups of patients with similar improvement patterns post therapy.

Goal II - Item-level analysis: To provide a deeper understanding of the differences in effectiveness between the three therapeutic approaches, this clinical trial will plan to explore item-level between-group differences in improvement.

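### GAS is a primary outcome in all four arms, but the plan does not ensure that its goals and expected levels are comparable between the ICF arm and the others

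*Combined protocol and SAP*

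**What the plan says.** Sections 1 and 2.5.1 name GAS, PROMIS Global Health and WHODAS 2.0 as primary outcomes, with no restriction by arm. Section 2.5.1 describes the instrument: "GAS is an individualized outcome measure involving goal selection and goal scaling". It defines a Global goal, a Program goal and three Cycle goals. The Program goal is framed by what the rehabilitation programme can deliver, and the Cycle goals are evaluated by the rehabilitation team with the patient.

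Goal setting as an activity is described for Group 1 only, in section 2.3:
- It follows allocation: "Patients randomized to the GROUP 1 will undergo a multidimensional assessment, a functional profile will be created and the individual goals and intervention proposed".
- It is joint work of the treating team and the patient: "The interdisciplinary team together with the patient will use the functional profile to define in detail the overall goal and sub-goals".
- It steers treatment. Time with each specialist depends on the goals, and the team meets weekly to "evaluate the fulfilment of the set goals and to adjust therapeutic procedures so that the goals of the therapy are best met".

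For Groups 2 and 3 the same section says: "Efforts of the different team members are parallel and discipline oriented". For Group 4: "A comparative group will undergo standardly provided care at department of neurology including face to face physiotherapy". Neither description contains a goal-setting step.

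Hypothesis II (section 2.8) expects the ICF arm to have the highest impact on the primary outcomes and "on such secondary outcomes that were identified as treatment goals". Section 2.9 tests this by comparing the ICF group with all other participants, one-sided.

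On timing, section 2.2 places randomisation within 48 hours of admission, and section 2.4 places baseline testing on days 2 and 3. Section 2.4 also says that the study examiners do not know the treatment group, and Table 2 lists GAS after the Psychologist heading.

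**The concern.** A GAS score measures attainment relative to a target written for one patient. A between-arm comparison is interpretable only if targets are chosen and scaled in the same way in every arm by people who do not know the arm. The plan does not state this. It describes an arm in which agreeing goals, and steering therapy towards them, is the intervention, beside three arms for which it describes no goal setting.

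If expected levels are easier, or goals better suited to the treatment, in the ICF arm, that arm gains on GAS with no better recovery. Hypothesis II tests in exactly that direction, so the error would appear as a positive finding on a primary outcome. Later analysis cannot repair it, because adjustment cannot recover the goal that a patient would have had under a common procedure.

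The secondary part of Hypothesis II has a related gap. It refers to outcomes identified as treatment goals, but the plan does not say who identifies them, when, or in which arms.

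**Working it through.** **1. Could goals be set differently by arm while the plan is followed?**

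| Question | Group 1 | Groups 2 and 3 | Group 4 |
|---|---|---|---|
| Goal-setting step described (2.3) | Yes, after allocation | No | No |
| Who sets goals | Treating team with patient | Not stated | Not stated |
| Therapy steered to goals | Yes, weekly review | Not stated | Not stated |

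Section 2.5.1 fills none of these gaps. It names the goal types but not the setter, the timing relative to allocation, or how difficulty is made equal. Its framing of the Program goal by what the programme can achieve lets the expected level vary with the treatment received. Evaluation of the Cycle goals by the rehabilitation team has no described counterpart in Group 4.

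Timing does not close the gap. With randomisation by 48 hours and baseline testing on days 2 and 3, baseline work can follow allocation. So the answer is yes.

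**2. How much could this matter?** The documents give no estimate of a difference in goal difficulty, so the shift *b* (in SD of GAS) is assumed and varied.

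Sample size, from section 2.6: d = 0.5, alpha 0.05, power 0.80, 70 per group, 210 in total. The usual two-sided formula gives n = 2(1.960 + 0.842)² / 0.5² = 62.8, so 63 per group (64 with the t distribution). The stated 70 is higher, with power of about 0.84. It equals 63/0.9, but no dropout allowance is stated. Four arms of 70 make 280, not 210, and 210 over four arms is 52.5 each, so both sizes are used below.

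Test, from section 2.9: ICF against the rest, one-sided. The nominal 5% level is taken from section 2.6. With no true effect:

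- SE = √(1/n₁ + 1/n₂), in SD units
- rejection probability = Φ(b/SE − 1.645)

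For 70 against 210: SE = √(1/70 + 1/210) = 0.138. At b = 0.2: Φ(1.449 − 1.645) = Φ(−0.196) = 0.42.

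For 52.5 against 157.5: SE = √(1/52.5 + 1/157.5) = 0.159. At b = 0.2: Φ(1.255 − 1.645) = Φ(−0.390) = 0.35.

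| Assumed shift b (SD) | 70 vs 210 | 52.5 vs 157.5 |
|---|---|---|
| 0 | 5% | 5% |
| 0.1 | 18% | 15% |
| 0.2 | 42% | 35% |
| 0.3 | 70% | 59% |
| 0.5 | 98% | 93% |

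If the rest is read as only the other two intensive arms, b = 0.2 gives 39% (70 vs 140) and 32% (52.5 vs 105). The conclusion does not turn on that reading.

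**The case against.** The strongest reply is that the documents never say that Group 1's GAS goals are its ICF therapy goals. Section 2.3 describes therapy goals, while section 2.5.1 describes GAS goals without naming an arm. Table 2 lists GAS after the Psychologist heading, and a psychologist is among the blinded examiners. On that reading GAS goals could already be set blind and alike in all arms. This stands in part: a reader might infer that the scores are not comparable, or that the treating team writes the GAS targets, and the text supports neither. What remains is that nothing keeps the two sets of goals apart, and examiner blinding is stated for assessment, not for goal setting. The GAS row shows no visit marks in the text available, which may be an extraction fault and is given no weight.

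Second, goals are agreed with the patient. That is correct. A reader might infer that the team deliberately sets easy targets, but nothing documents this. Knowledge of the arm and of what the programme offers is enough to shift expectations.

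Third, a reader might infer that the goal-related secondary comparison sets ICF patients, selected on their worst domains, against unselected patients, so that regression to the mean favours ICF. Section 2.9 specifies no goal-matched subset, and section 2.1 ties Group 1 treatment to needs and wishes, not to the worst score. The supportable point is that the identification of these outcomes is undefined.

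Fourth, the size is hypothetical. That is accepted. Section 2.5.1 gives only a five-point rating and defines no composite of all five goals at any visit, so a conversion into GAS points would rest on assumptions about the score as well as the shift. The d = 0.5 in section 2.6 comes from the Berg Balance Scale and is not a benchmark for GAS.

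**Conclusion.** The concern holds in this form: comparability of GAS goals and expected levels between arms is not ensured. The plan can be followed to the letter and still let goal choice and difficulty differ by arm, in the direction that Hypothesis II tests. This is more than a missing detail, because the one arm with a described goal-setting process sets its goals after allocation and builds treatment on them.

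The documents do not show that a bias exists or how large it would be. The error rates are illustrations that assume no true effect, a pure shift in GAS, the normal approximation and a nominal one-sided 5% level. Under those assumptions a shift of 0.2 SD is enough to bring the chance of a false ICF advantage on GAS to about 35% to 42%.

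The scope is limited to GAS and to the goal-related secondary part of Hypothesis II. PROMIS and WHODAS 2.0 do not depend on goal selection and are unaffected by this point.

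**What to change.** In sections 2.4 and 2.5.1, state for all four arms:

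1. The same allocation-blind study examiner sets and scales the GAS goals with the patient at the baseline assessment. The psychologist is the natural choice, given where GAS sits in Table 2.
2. This is done before allocation is disclosed to the patient or the treating team where the 48-hour window allows, and otherwise by an examiner unaware of allocation.
3. Goals and expected levels are locked in the eCRF, and GAS is scored only against them. The ICF team keeps its own therapy goals.
4. At the same interview, the examiner records for every patient which secondary outcomes match the goals. The goal-related part of Hypothesis II is tested only in goal-matched patients of every arm.

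The cost is protocol wording and a fixed order of baseline steps, using an examiner already in the trial. The windows in sections 2.2 and 2.4 are tight, so goal setting before disclosure may not be possible for everyone. Under the fallback the patient may already know the arm, which is weaker protection. Locked goals may also differ from those the ICF team later works on, so the ICF effect on GAS may look smaller. If a common procedure is not feasible, GAS should not serve as a between-arm primary outcome.

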2.1. Clinical trial design

This will be a Four-Arm Parallel-Group Randomised Double Blinded Controlled Trial with a longitudinal design. Patients who fulfilled inclusion criteria will be randomly assigned to one of the four research groups (Group 1, 2, 3 or 4). Three groups will undergo an inpatient COMIRESTROKE (4 hours/day for 3 weeks). Group 1 (COMIRESTROKE – ICF) will undergo individualised rehabilitation therapy embodying the ICF system as a therapeutic tool, where current needs and wishes of the person after IS are integrated into an interdisciplinary team rehabilitation programme management. Group 2 and 3 will undergo a standard comprehensive intensive rehabilitation program three hours per day (39) plus one hour of specific PT (an individual neuroproprioceptive "facilitation inhibition" for Group 2, a technology-based training for Group 3). Group 4 will undergo standard care and will serve as comparative one to the intensified intervention groups.

Participants will be examined four times (Figure 1). At the beginning and after three weeks of hospitalization (both primary, secondary outcomes and a blood draw will be obtained for total RNA extraction, cDNA synthesis and real-time QPCR assessment of lncRNA candidates previously identified as potential therapeutic influencers in ischemic stroke), and then three months and one year after the end of the program (primary outcomes only).

Figure 1: Design of the study

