2.4. Pre- and post-intervention assessments

Once an informed consent is obtained prior to randomisation; participants will be referred to study examiners - a Physical Medicine and Rehabilitation physician, a neurologist, a physical therapist, an occupational therapist and a psychologist, who will not know the treatment group of the patient. They will administer baseline testing during the 2nd and 3rd day after admission to the department (Pre-assessment). The Post-assessment 1 will be done at the end of the three-week inpatient intensive comprehensive rehabilitation (during the last two days of hospitalization). Follow-up assessments will take place 3 and 12 months after the admission, respectively, by a telephone interview and hospital visit for blood draw. The aim is to be assessed only by one examiner, in case of more examiners, inter-rater reliability will be assessed (Table 2).

test	abbreviation	Inclusion and exclusion criteria	Examination No			
			1	2	3	4
			baseli	+3	+3	+ 1
			ne	weeks	month s	year
Neurologist						
Demographic and anamnestic data (age, after first ischemic stroke, days after the stroke) Demographic and anamnestic data (weight and height, cardiovascular risk factors, Bamford classification, medication)			x			
Modified Rankin Scale	mRS	Х		х		
Pre-Stroke Modified Rankin Score	pre-stroke mRS	Х				
Historic Stroke Motor Severity Score	HSSS	Х				
National Institute of Health Stroke Scale	NIHSS	Х				
Psychologist*						
Montreal Cognitive Assessment	MoCA		Х			
Amnesia Light and Brief Assessment	ALBA		х	х		
NEO-Five Factor Inventory	NEO - FFI		х			
Patient-reported Outcomes Measurement Information System Global Health	PROMIS		х	х	х	х
the World Health Organization Disability Assessment Schedule	WHODAS		Х	Х	Х	Х

Table 2: Timing and distribution of examination in the team

the Goal Attainment scale	GAS				
Picture naming and immediate recall	PICNIR	х	х		
Neuro - QOL depression		х	х		
physical therapist					
Hand Dynamometer		Х	Х		
postural tremor		х	х		
Action Research Arm Test*	ARAT	х	х		
Motor Activity Log*	MAL	х	x		
Timed Up and Go*	TUG	х	x		
Berg Balance Scale*	BBS	х	x		
The 10 Metre Walk Test*		x	х		
The 6 Minute Walk Test*		x	х		
Functional Independence Measure*	FIM	х	х		
Laterality index	LI	х			
Nine Hole Peg Test		х	х		
speech therapist*					
The Gugging Swallowing Screen	GSS	Х	х		
The 3F Test – Dysarthric Profile	3F test	х	х	-	
Dysan		х	х		
The Mississippi Aphasia Screening	MAST	х	х		
Test					
Image Naming Test	INT	Х	X		

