Blood – Total RNA extraction		х	х	-	
cDNA synthesis					
lncRNA assessment (C2dat1 , GAS5 ,					
MALATI, PARTICLE, H19, MEG3)					

*Tests recommended by General Health Insurance (GHI), Czech Republic.

The qualitative data will be collected in semi-structured interviews with patients as well as clinical specialists with the aim of capturing an extended health evaluation. Specialists will have the possibility to look at the hospital information system, or search in the National Register of Paid Health Services. Data will be captured using an electronic Case Report Form (eCRF) (65).

The following data will be collected:

Demographic and anamnestic data including personal factors (sex, age, education, occupation, social relations, living situation), weight and height, laterality index (66), number of days after the stroke event, personality based on the NEO-Five Factor Inventory (NEO-FFI) (67), pre-stroke functional status based on modified Rankin Scale (68), cardiovascular risk factors (69), the degree of neurological impairment according to the National Institute of Health Stroke Scale (70) and disability with the Modified Rankin Scale (42), Bamford classification of IS based on the initial presenting symptoms and clinical signs (71) as well as pharmacotherapy.

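### No arm has planned recording or analysis of harms, and the phone collection of post-discharge care appears only in the Group 2 and 3 text, with unclear scope

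*Combined protocol and SAP*

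**What the plan says.** Group numbers below follow section 2.3; section 2.1 attaches the technology and neuroproprioceptive programmes to Groups 2 and 3 the other way round.

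- Entry (section 2.2): patients must be judged "with a potential to accept 4 hours of comprehensive rehabilitation per day and to profit from the physiotherapy".
- After discharge, Group 1 (section 2.3): "participants will be referred and to a short-term outpatient rehabilitation programme".
- After discharge, closing the Group 3 paragraph under the joint Group 2 and 3 heading (section 2.3): "After finishing this intensive complex inpatient program COMIRESTROKE, participants will undergo standard/not directed treatment offered by the Czech Health Care system". The next sentence says that information "as to the health and social care the rehabilitant received after hospitalisation will be collected by phone call".
- Group 4 (section 2.3): "A comparative group will undergo standardly provided care at department of neurology including face to face physiotherapy". Nothing is said about the period after discharge.
- Follow-up (section 2.1): examinations "three months and one year after the end of the program (primary outcomes only".
- Follow-up (section 2.4), not restricted by arm: "Follow-up assessments will take place 3 and 12 months after the admission, respectively, by a telephone interview and hospital visit for blood draw".
- Other sources (section 2.4), also not restricted by arm: qualitative interviews with patients and staff, and "Specialists will have the possibility to look at the hospital information system, or search in the National Register of Paid Health Services".

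**The concern.** Group 4 is there to be compared with three intensified programmes, in first-stroke patients aged up to 85. A claim that intensive rehabilitation is better needs a harm side as well as a benefit side. Information that no form asks for cannot be recovered at the analysis stage.

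The second issue concerns efficacy. Hypothesis II in section 2.8 predicts that Group 1 does best on the primary outcomes at follow-up, and Group 1 is the one arm with a stated outpatient referral. If services used after discharge are documented in some arms and not in others, a Group 1 advantage at 12 months could come from the inpatient programme, from the outpatient care that followed, or from both. The data would not show which.

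**Working it through.** No figure in the plan bears on harms, so the check is mainly a reading of sections 2.1 to 2.10.

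**Step 1. Where harms could be recorded or analysed**

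| Place | Content on harms |
|---|---|
| Table 2, four examinations | No row for death, recurrent stroke, readmission, falls or early stopping; NIHSS is marked for eligibility only |
| 2.5 Outcomes | No safety outcome among primary, secondary or other measures |
| 2.7 to 2.9 Statistics and hypotheses | No harm hypothesis, summary or test |
| 2.3 Delivery of treatment | Treatment is logged by insurance codes, so a shortfall could be seen; no field for the reason |

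Planned harm recording is therefore absent in four of four arms.

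**Step 2. Routes by which an event might still surface**

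- The 3- and 12-month contacts reach every arm, but section 2.1 limits their content to primary outcomes.
- The interviews have no stated harm items.
- The hospital-record and register lookup is permitted, not required, and has no event list or time window.

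An event may come to light by any of these routes, but none does so in a fixed way that is the same across arms.

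**Step 3. Scope of the phone-call sentence**

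The sentence names no group. With 1:1:1:1 allocation (section 2.2), the share of patients not covered is (4 − arms covered) / 4:

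| Reading | Arms covered | Share not covered |
|---|---|---|
| Group 3 only (the paragraph it closes) | 1 | 3/4 = 75% |
| Groups 2 and 3 (the heading it falls under) | 2 | 2/4 = 50% |
| All COMIRESTROKE patients (the programme named just before) | 3 | 1/4 = 25% |

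Group 4 never enters COMIRESTROKE and is outside all three readings. Group 1 is covered only by the third. Shares are used because section 2.6 gives both 210 patients in total and 70 per group, and four groups of 70 make 280.

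**Step 4. What harm counts could show if collected**

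Take n₁ patients in Group 4 and n₂ = 3n₁ in the pooled intensive arms, two-sided α = 0.05, and power = Φ[(|p₂ − p₁| − 1.96·SE₀)/SE₁], where SE₀ uses the pooled rate and SE₁ the separate rates. Event rates are not in the documents; those below are assumptions.

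Example: n₁ = 70, n₂ = 210, p₁ = 5%, p₂ = 10%.

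- Pooled rate = (3.5 + 21)/280 = 0.0875.
- SE₀ = √[0.0875 × 0.9125 × (1/70 + 1/210)] = 0.0390.
- SE₁ = √[0.0475/70 + 0.09/210] = 0.0333.
- Power = Φ[(0.05 − 0.0764)/0.0333] = 0.21.

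| Group 4 rate vs intensive rate | n₁ = 70 | n₁ = 52 (210/4 = 52.5, rounded down) |
|---|---|---|
| 5% vs 10% | 0.21 | 0.16 |
| 10% vs 20% | 0.48 | 0.36 |
| 5% vs 15% | 0.62 | 0.46 |

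Counts by arm would be descriptive. That is enough reason to collect them, but not to add a formal test.

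**The case against.** The strongest reply is that the trial is not blind to events. Every arm is contacted at 3 and 12 months, patients and staff are interviewed, and records and a national register can be consulted. Repeat FIM and Berg Balance at three weeks would show some functional worsening. Insurance coding shows treatment delivered, and Group 1 has weekly team review. All of this stands, and it rules out saying that harms cannot be compared at all, or that intolerance of the programme goes unrecorded. What remains is that none of these sources names an event, and no field holds the reason a programme was cut short.

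A reader might also infer that events are captured in Groups 2 and 3 and missed elsewhere, so that an event table would be biased against those two arms. The documents do not support that. The call asks about services received, which indicates harm only indirectly. Its restriction to Groups 2 and 3 is inferred from where the sentence sits. No event table is planned that could be biased. For the same reason, and because the documents give no event rate, a count of events missed cannot be supported.

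Finally, the Group 1 referral may be intended as part of that strategy. Randomisation then still supports a comparison of whole strategies. It does not support crediting a later difference to the inpatient content, and readers would still need to know what care the other arms received.

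**Conclusion.** The concern holds in two parts. First, no arm has scheduled recording or analysis of death, recurrent stroke, readmission, injurious fall, neurological worsening or early stopping. The trial therefore has no planned, systematic comparison of harms between 4 hours a day of rehabilitation and standard care. Second, the collection of post-discharge care is described in one place with unclear scope. It leaves out 25% to 75% of patients depending on the reading, and Group 4 on every natural reading. Differences at 3 and 12 months therefore cannot be separated from care after discharge.

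This rests on the text of sections 2.1 to 2.10, which run without a visible gap, and on the assumption that Figures 1 and 2 (design and recruitment flow), which could not be read, add no harm recording. It does not depend on any assumed event rate. It should be corrected while data can still be collected.

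**What to change.** - Move the phone-call sentence from the Group 3 paragraph to section 2.4 and state that it applies identically to all four groups at the existing 3- and 12-month calls.
- Use one fixed script: care received since discharge (including outpatient rehabilitation), death and its date, recurrent stroke, readmission, and injurious fall. Ask these items after the primary outcome questions, so that an answer hinting at allocation cannot colour those ratings.
- Add a Table 2 row for these events at 3 and 12 months, and a three-week entry for falls, neurological worsening, and programme stopped early with the reason.
- Use the hospital-record and register lookup already named in section 2.4 in the same way in every arm for patients who are not reached.
- Report counts by arm, without a formal test.
- Reconcile the follow-up anchor, which is the end of the programme in section 2.1 and admission in section 2.4, so that the event window is the same for everyone.

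The cost is a few minutes per call and some protocol and eCRF wording. The calls and data sources are already in the plan, and the sample size and primary analysis do not change.
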